With support from the National Immunization and Vaccines Development (IVD) program of the Tanzanian National Ministry of Health, Community Development, Gender, Elderly and Children, we are evaluating the efficacy of mobile phone-based vaccination reminders and incentives in the form of conditional financial transfers (CFTs) for offsetting demand-side barriers to timely vaccination. Per the recently released WHO classification of digital health interventions, the two key interventions in this study correspond to 1.1 Targeted client communication (specifically, 1.1.3 Transmit targeted alerts and reminders to clients), and 1.7 Client financial transactions (specifically, 1.7.3 Transmit or manage incentives to clients for health services.) [34] Our hypothesis is that reminders and incentives will increase timeliness of vaccinations relative to the status quo. The design and protocol of the evaluation are described below.

Methods/Design

Study aim

The aim of the study is to assess the efficacy of (1) mobile phone-based reminders, and (2) mobile phone-based reminders combined with incentives in the form of CFTs, for improving vaccination timeliness among children at 6, 10 and 14 weeks after birth, compared to the standard of care.

Outcome measures

The recommended schedule for vaccinations by age 1 year is presented in **Table 1**. The primary study outcome is whether or not a child received an on-time vaccination; the outcome is measured for vaccinations scheduled at 6, 10 and 14 weeks after birth. Secondary outcomes include vaccination coverage, in aggregate and for each of the vaccinations due at 6, 10 and 14 weeks after birth. Timeliness is defined as vaccination within 28 days of the scheduled vaccination due date. Coverage is defined as the percentage of children vaccinated.

Study design

The study design represents a quasi-randomized controlled trial that includes three phases, each corresponding to one study arm: 1) standard of care (no reminders or incentives); 2) mobile phone-based reminders; and 3) mobile phone-based reminders combined with incentives in the form of CFTs. Arm 1 serves as the control arm; arms 2 and 3 are intervention arms. The trial is enfolded by base- and end-line assessments (**Figure 1**).

Assignment to study arms and transitions between arms

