Women providing informed consent are enrolled in the study. At the time of enrollment, a baseline survey is conducted with all participants to assess socio-demographic characteristics, mobile phone ownership and use, reproductive history, EDD for the current pregnancy, and vaccination knowledge, history of vaccinations in a prior child, if applicable, and previously experienced or anticipated barriers to vaccinations. Mobile phone numbers are obtained for mothers and any authorized agents. Surveys are implemented electronically on tablet devices

and conducted by study staff at health facilities, participants' homes, or other mutually agreed-upon locations.

Toward the end of Phase 1, all women are contacted by phone to ascertain birth dates and outcomes, and information on past and scheduled vaccinations. The information is used to generate child-specific vaccination schedules. In Phases 2 and 3, reminder messages are sent to registered mobile phone numbers 1 week and 1 day prior to each scheduled vaccination, and, if no vaccination confirmation is received, 2 weeks after the vaccination due date. Uniquely numbered cards, given to participants at each completed or rescheduled vaccination, allow participants to report vaccination dates via the USSD system. When no vaccination report is received via the USSD system, SMS, or phone calls from participants, study staff contact the participant by phone to verify whether and when a vaccination was received, and ascertain the due date for the next vaccination, if applicable. Recorded vaccination dates are used to iteratively update vaccination schedules and to re-schedule reminders.

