During Phase 3, reminder messages offer an incentive for each timely vaccination. The full incentive amount (TSH 2000; approximately \$0.90) is paid when a vaccination is received within 2 weeks (14 days) of the due date; half the incentive is paid if the vaccination is completed more than 2 weeks but within 4 weeks (28 days) after the vaccination due date. Incentive amounts are paid if the mother, despite going to the health facility as reminded, is asked to return for a vaccination at a later date. Payments for timely vaccinations are made via an SMS message that includes a network-specific mobile phone airtime recharge voucher code and is sent to a phone number specified by the mother. An in-person end-line survey, conducted 12 months after enrollment, assesses barriers to vaccinations, receipt and acceptability of reminders (Arms 2 and 3) and incentives (Arm 3), and records vaccination dates from participants' government-issued vaccination cards, allowing for comparisons with the data recorded in the mHealth system.

Data management

Password protected tablet devices are used to collect survey data from participants. Data transfer agreements (DTAs), signed by all participating institutions, guide the secure sharing of data between Tanzania and foreign collaborators. To ensure confidentiality, identifying information are collected, transferred, and stored separately from survey data. On-site study monitoring, performed by the Principal Investigators or their designees, is used to verify

compliance with human subjects and other research regulations and guidelines, assess adherence to the study protocol, and confirm the quality and accuracy of information collected and entered into the study database. All collaborators have access to the final data.

Statistical analysis

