For each participant, outcomes are observed at three time points (corresponding to timely vaccinations at 6, 10 and 14 weeks, respectively). The probability of timely vaccinations and its association with reminders and incentives will be analyzed using a random effects logistic regression model. The outcome variable is 1 if the vaccination was received on-time, and 0 if early, delayed, or not received at all. The primary covariates of interest are indicator variables for the receipt of reminders only (“*reminder*”) and the receipt of reminders with an incentive offer (“*reminder+incentive*”). For arm 1 the value of both covariates is 0 for all three time points. For outcomes in arm 2, the value for *reminder* (and for arm 3 the value for *reminder+incentive*) is 1 if the mHealth system confirmed delivery of the reminder, and 0 for all other observations. Additional covariates (e.g. mother’s education, rural vs. urban residence, recruitment from health facilities vs. the community) will control for differences in participant characteristics between study arms and their association with vaccination timeliness. Interactions of *reminder* and *reminder+incentive* with these covariates describe systematic variation in the effects of reminders and incentives on vaccination timeliness. Models will control for the number of phone-based contacts prior to or within the timeliness window for any given vaccination, and standard errors will be adjusted to account for clustering at the level of the health facility catchment area.

Statistical power

Across 400 participants we expect up to 1,200 data points on vaccination timeliness. Assuming (a) that these data points are distributed equally across the 3 study arms (standard of care; reminders only; reminders and incentive); (b) a 10% attrition rate; (c) equal cluster sizes of 10 women per health facility catchment area, with an intra-cluster correlation of 0.02; (d) 3 observations per child, with a within-child correlation of 0.2; (e) a baseline rate of vaccination timeliness of 65% in the control condition; and (f) a 10 (15) percentage point difference associated with reminders (reminders and incentives), the power ($\alpha=.05$, 2-tailed) to detect such difference is 72% (98%).

Dissemination

Results will be shared with stakeholders at the regional and national levels, presented at national and international conferences, and published in high impact academic journals.

Data sharing

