Efforts will be made to develop a data repository for the storage of de-identified study data. Investigators wishing to use study data to answer new research questions may submit data analysis concept proposals for consideration by the Principal Investigators. The Principal Investigators will review the proposal and will provide those submitting scientifically rigorous and promising proposals access to the data repository to address their research questions.

Discussion

This study examines the efficacy of mobile phone-based reminders and incentives in the form of conditional financial transfers for offsetting demand-side barriers to timely childhood vaccinations in Tanzania. Our implementation strategy has several unique components, including the use of a USSD-based birth and vaccination event notification system, an adaptive schedule for vaccination reminders which is derived from the date of the preceding event, a tiered incentive system, and the automated disbursement of mobile phone credit for eligible timely vaccinations.

The study is subject to several limitations: First, feasibility considerations limit the study area to include only health facilities and their catchment areas within approximately 30 km of Mtwara municipality. More remote populations may face additional barriers that cannot be evaluated in this study. Second, only women with access to mobile phones are included in the study. To minimize selection bias, women could designate anyone with a mobile phone to be their study contact. However, for women relying on such authorized agents, receipt of messages and payments for timely vaccinations could remain a challenge. Third, reminder schedules and payments for timely vaccinations are based on client-reported birth and vaccination dates. The dependence on client reports may introduce delays, affect schedule accuracy, and motivate inaccurate reporting of vaccination dates. Comprehensive quality control, including automated alerts to study staff for participant follow-up, algorithms that identify inconsistencies in near real time, and an in-person end-line survey with a review of government-issued vaccination cards, will be used to assess and/or mitigate these concerns. Fourth, it is plausible that follow-up phone calls by study staff to ascertain birth outcomes, the timing of past vaccinations, and/or the

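### Neither document says which record supplies the vaccination and due dates for the primary outcome, so payment-linked participant reports can define it and inflate the incentive effect

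*Protocol*

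**What the plan says.** The outcome is defined without a data source. Protocol, Outcome measures: "Timeliness is defined as vaccination within 28 days of the scheduled vaccination due date". Protocol, Statistical analysis, with the same sentence in the SAP: "The outcome variable is 1 if the vaccination was received on-time, and 0 if early, delayed, or not received at all". Neither says whose record of the vaccination date, or of the due date, is used.

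Protocol, Study activities, describes how dates arrive during follow-up:
- Toward the end of Phase 1, staff phone all women about births and about past and scheduled vaccinations.
- After that, "Uniquely numbered cards, given to participants at each completed or rescheduled vaccination, allow participants to report vaccination dates via the USSD system". SMS and calls from participants are also accepted.
- Where no report comes in, "study staff contact the participant by phone to verify whether and when a vaccination was received".

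The same section offers payment in Phase 3 only: the full amount up to 14 days after the due date and half up to 28 days.

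Protocol, Discussion (limitations), states that "reminder schedules and payments for timely vaccinations are based on client-reported birth and vaccination dates", and that this dependence may "motivate inaccurate reporting of vaccination dates".

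Card dates appear twice. Study activities has the 12-month end-line survey record vaccination dates from government-issued cards, "allowing for comparisons with the data recorded in the mHealth system". The limitations text lists card review, automated staff alerts and inconsistency algorithms as ways to gauge or reduce the reporting problem. The SAP does not mention cards.

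**The concern.** The late limit for payment, 28 days after the due date, is also the late limit of the primary outcome. In arm 3, a report that moves a late vaccination inside the window both earns airtime and turns a 0 into a 1. In arms 1 and 2 such a report earns nothing. If reported dates define the outcome, misclassification can differ by arm and would be read as an effect of the incentive.

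The planned covariates (education, residence, recruitment route, number of phone contacts) do not measure this. The motive follows the incentive offer, and so largely the reminder+incentive indicator itself.

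The due date is exposed too. Under the scheduling system (Protocol, Intervention components and implementation), a delayed vaccination moves the later due dates by the same delay. A wrong reported date can therefore also shift the yardstick for the next event.

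**Working it through.** **1. What the documents fix and what they leave open**

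| Item | Stated? | Where |
|---|---|---|
| Window for on-time | Yes, 28 days | Outcome measures |
| Record giving the vaccination date for the outcome | No | Outcome measures; Statistical analysis; SAP |
| Record giving the due date for the outcome | No | same |
| Route of dates during follow-up | Participant report | Study activities |
| Arm in which a timely date is paid | Arm 3 only | Study activities |
| Role of card dates | Comparison; quality control | Study activities; Discussion |
| Precedence when sources disagree, missing cards, card-based analysis | No | nowhere |

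An analyst who takes the mHealth dates complies with the plan. So does one who takes the card dates.

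**2. Inputs for an illustration (Protocol, Statistical power)**

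- Up to 1,200 data points, equally split: 1,200/3 = 400 per arm. With 10% attrition: 400 × 0.9 = 360.
- Clusters of 10 women, ICC 0.02: 1 + 9 × 0.02 = 1.18.
- 3 observations per child, correlation 0.2: 1 + 2 × 0.2 = 1.40.
- Product: 1.18 × 1.40 = 1.652. Effective n per arm: 360/1.652 ≈ 218. With the within-child term alone: 360/1.40 ≈ 257.
- Control rate 65%, so 35% are non-timely: 360 × 0.35 = 126 events per arm.

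The plan's own figure is power of 72% (98%) for differences of 10 (15) points. A two-proportion calculation gives 62.5% (94.2%) at 218 and 69.8% (97.0%) at 257. The protocol gives no formula, and crediting within-child comparisons across arms could explain the gap. I do not call the stated power wrong, and nothing below depends on it. The two sample sizes serve only as a range.

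**3. False gain with no true effect**

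Let m be the share of truly non-timely arm 3 events reported as timely, with no misreporting in arm 1 and a true rate of 65% in both arms. The documents give no value for m, so the values below are assumptions.

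Apparent arm 3 rate = 0.65 + 0.35 × m. False gain = 35 × m points.

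The chance of a significant result is from a pooled two-proportion z test, two-sided 5%. With d = 0.35 × m, s0 the pooled and s1 the unpooled standard error, it is 1 − Φ((1.96 × s0 − d)/s1) plus a negligible opposite tail. For m = 20% at 218: d = 0.07, s0 = 0.0445, s1 = 0.0444, giving 1 − Φ(0.39) ≈ 35%.

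| m | Events of 126 | False gain (points) | False significance, n = 218 | n = 257 |
|---|---|---|---|---|
| 5% | 6.3 | 1.75 | 7% | 7% |
| 10% | 12.6 | 3.5 | 12% | 13% |
| 20% | 25.2 | 7.0 | 35% | 40% |
| 30% | 37.8 | 10.5 | 67% | 74% |

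Producing the whole planned 15-point effect this way would need m = 15/35 ≈ 43%.

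**4. Simplifications**

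This is a crude comparison of arms, not the planned mixed model. It ignores undelivered reminders, which are coded as unexposed. The 35% also contains early vaccinations, which the outcome codes 0 and for which the payment motive is less clear.

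**The case against.** A fair defence has four parts.

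*The protocol sees the risk and plans a response.* This stands in part. It names inaccurate reporting and lists card review among the measures to assess or reduce it. A reader might infer that card dates serve only for comparison; the limitations text does not support that. It is, however, a quality-control intention: it permits assessment without any change to the outcome, and the SAP is silent.

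*The plan never says that the outcome rests on reports.* Correct. The limitations text applies client reporting to reminder schedules and payments, not to the outcome. A reader might infer that the trial has committed to a biased analysis. It has not; the source is left open.

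*Arm 3 error need not be large, or run one way.* Also correct.
- The numbered cards handed out at a visit are a partial check that the visit occurred, though nothing shows that they verify its date.
- Mothers who attend and are asked to return are paid anyway, so that group has no payment motive to alter a date.
- The full amount is about $0.90.
- Retrospective Phase 1 reports can err in either direction. An understated delay also sets the next due date too early, which works against an on-time result at the next event.

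The claim that error certainly runs upward and only in arm 3 is therefore not supported. Upward error is what the payment would be expected to encourage.

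*Ascertainment is broadly shared across arms.* Largely true. All arms rely on participant report, and the USSD description is not limited to later phases. What clearly differs is the payment and, for Phase 1, the timing of the staff call.

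**Conclusion.** The concern holds as an unspecified outcome source with an avoidable risk of bias. A compliant analysis can use dates that earn payment in one arm only, over a window with the same late limit as the outcome. A source less exposed to that motive is already due to be collected but has no precedence.

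The size of any bias is unknown. The table in the working ranges from 1.75 points, with the error rate barely above 5%, to 10.5 points, with a false significant result more likely than not. It rests on assumed misreporting rates, a 65% true rate in both arms and accurate dates in arm 1.

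A reader might also infer that card dates will exist for everyone. The documents plan the end-line survey for participants generally, but they assume 10% attrition and do not address missing cards. This is a cheap improvement that should be made, not evidence that the result will be wrong.

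**What to change.** Add to the SAP:

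1. The vaccination date for the outcome is taken from the government vaccination card for every event in all three arms. Where sources disagree, the card date prevails.
2. A reported date is used only when no card is seen, under the same rule in every arm, and is flagged. A payment record alone does not count as evidence of vaccination.
3. The due date used for the outcome follows one stated rule in all arms that does not depend on unverified reported dates. This concerns the outcome definition only; the operational reminder schedule can stay as it is.
4. Agreement between card and reported dates is tabulated by arm.
5. The primary model is repeated on card-verified events only.

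Reported dates keep their role in triggering reminders and payments.

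Cost: mostly SAP wording, since card vaccination dates are already planned. The end-line text mentions vaccination dates only, so verifying the birth date may need one added field. Events without a card rely on the flagged fallback, which keeps some exposure to self-report, or drop out of the card-only analysis.

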Assignment to study arms is implemented at the level of the vaccination event, with all vaccination events scheduled during a phase assigned to the corresponding arm. T_1 , the beginning of Phase 1, denotes the time of participants' enrollment into the control arm. At time T_2 , the beginning of Phase 2, all participants are rolled over to the arm with reminders; at time T_3 , the beginning of Phase 3, all participants are rolled over to the arm with reminders combined with incentives. While T_2 and T_3 denote fixed points in calendar time, variation in delivery dates across participants results in between- and within-individual variation in the assignment of vaccination events across the three arms. **Table 2** shows all possible combinations of vaccination event assignments to study arms at the level of the participant. With dates of birth exogenously determining children's vaccination schedules, shifts in T_2 and T_3 directly affect the number of vaccination events that may be observed in each study phase. Based on the distributions of expected delivery and vaccination due dates, T_2 and T_3 are chosen such that the expected number of vaccination events is approximately equal across the three arms. With T_2 and T_3 being random in relation to mothers' delivery dates, and thus children's vaccination schedules, the assignment of vaccination events across arms may be considered quasi-random. Loss to follow-up and other reasons for non-delivery of vaccination reminders result in exposure indistinguishable from the control condition.

The assignment to study arms based on scheduled vaccination dates, and the simultaneous transition of all participants between study arms, address concerns that the individual randomization into, and co-existence of, incentive and non-incentive arms are not considered viable within closely-knit communities. While cluster randomization was considered as an alternative approach, the heterogeneity of clusters suggests that this approach would confound the effects of settings with the effects of reminders and incentives.

Study setting

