timing of the next scheduled vaccination, may themselves function as an intervention. Fifth, temporal changes that coincide with the points of transition between study arms could influence results. Finally, while the primary focus of the study is on demand-side barriers to timely vaccinations, participating health facilities may encounter vaccine stock outs and power outages, resulting in vaccination activities being deferred until vaccine stocks are received or power is restored. We plan to monitor these events along with mHealth system and mobile network metrics (e.g., message transmission errors, calls dropped) during the study period. By characterizing, and if possible, addressing the limitations of our study, we will provide critical information for the feasibility of scaling up reminders and/or incentives to the regional or national levels in low-resource settings such as Tanzania.

With the continuing diffusion of mobile phones and the ongoing development of mHealth technologies, adaptive programming in the form of dynamic reminder systems and variable incentive structures has become a feasible reality even in low-resource settings. Our study sheds light on the demand-side barriers to vaccinations and the synergistic potential of combining mHealth reminders and incentives for improving vaccination coverage and timeliness. The results have implications for the design and potential efficacy of other subsidy or incentive programs aimed at improving health and health seeking behaviors.

References

1. World Health Organization. *Immunization coverage*. 2016 September 2016 [cited 2016 November 07]; Available from: <http://www.who.int/mediacentre/factsheets/fs378/en/>.
2. World Health Organization, *Global Vaccine Action Plan 2011-2020*. 2013, World Health Organization: Geneva, Switzerland.
3. Global Immunization Division, Centers of Disease Control and Prevention, and World Health Organization, *Epidemiology of the unimmunized child: Findings from the peer-reviewed published literature, 1999-2009*. 2009.
4. World Health Organization. *Immunization, Vaccines and Biologicals*. 2017 [cited 2017 October 26]; Available from: <http://www.who.int/immunization/en/>.
5. The DHS Program. *Demographic and Health Survey, and Malaria Indicator Survey, Tanzania*. 2015-16 [cited 2017 June 09]; Available from: <https://dhsprogram.com/pubs/pdf/FR321/FR321.pdf>.

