mHealth-Assisted Conditional Cash Transfers to Improve Timeliness of Vaccinations (MINT)

ClinicalTrials.gov ID NCT03252288

Statistical analysis

For each participant, outcomes are observed at three time points (corresponding to timely vaccinations at 6, 10 and 14 weeks, respectively). The probability of timely vaccinations and its association with reminders and incentives will be analyzed in a bivariable analysis and using a random effects logistic regression model. The outcome variable is 1 if the vaccination was received on-time, and 0 if early, delayed, or not received at all. The primary covariates of interest are indicator variables for the receipt of reminders only (“*reminder*”) and the receipt of reminders with an incentive offer (“*reminder+incentive*”). For arm 1 the value of both covariates is 0 for all three time points. For outcomes in arm 2, the value for *reminder* (and for arm 3 the value for *reminder+incentive*) is 1 if the mHealth system confirmed delivery of the reminder, and 0 for all other observations. Additional covariates (e.g. mother’s education, rural vs. urban residence, recruitment from health facilities vs. the community) will control for differences in participant characteristics between study arms and their association with vaccination timeliness. Interactions of *reminder* and *reminder+incentive* with these covariates describe systematic variation in the effects of reminders and incentives on vaccination timeliness. Models will control for the number of phone-based contacts prior to or within the timeliness window for any given vaccination, and standard errors will be adjusted to account for clustering at the level of the health facility catchment area.

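### Arms are calendar phases, but the stock-outs and power outages to be monitored have no place in the model, so long interruptions that differ between phases would be counted as intervention effects

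*Protocol*

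**What the plan says.** **Assignment.** The protocol section on assignment and transitions places events in arms by due date, with "all vaccination events scheduled during a phase assigned to the corresponding arm". The boundaries are common to everyone: "While T_2 and T_3 denote fixed points in calendar time", it is the spread of delivery dates that distributes events over the arms.

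**Outcome.** Timeliness means vaccination within 28 days of the due date (protocol, Outcome measures). An early, late or missed vaccination is coded 0, and the cause plays no part (Statistical analysis in both documents).

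**Known threats.** The Discussion states that "temporal changes that coincide with the points of transition between study arms could influence results" and that "participating health facilities may encounter vaccine stock outs and power outages, resulting in vaccination activities being deferred". Its response to the supply problem is "We plan to monitor these events along with mHealth system and mobile network metrics", followed by a general intention to characterise the limitations and address them if possible.

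**Model.** The SAP's random effects logistic model contains the two exposure indicators, further covariates that "will control for differences in participant characteristics between study arms", interactions with these, the number of phone contacts, and standard errors clustered by catchment area. The SAP also names a bivariable analysis. There is no supply, facility or calendar-time term, no exclusion of affected events and no sensitivity analysis.

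**The concern.** When everyone changes arm on the same date, whatever differs between phases differs between arms. A supply interruption is such a factor. It affects the outcome directly, and reminders to 400 women in districts of about 246,000 people (115,132 + 130,757) cannot plausibly cause it. It is therefore a confounder, and adjusting for it removes none of the intervention effect.

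The listed covariates (education, residence, recruitment route) are fixed traits of the mother and cannot represent an event at a facility in a given week. Clustered standard errors change the stated precision, not the bias.

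Two features of the plan make the gap more visible. The limitation listed just before the one on temporal change, that staff phone calls may act as an intervention, is carried into the model through the phone-contact covariate; the supply limitation is monitored too but gets no term. And the incentive is paid when a mother attends but is asked to come back later, so for payment the plan separates facility-caused delay from the mother's behaviour. The outcome does not, although the stated target is demand-side barriers.

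At stake is the primary estimate. An interruption in Phase 1 would inflate both effects; one in Phase 2 or Phase 3 would dilute or reverse the effect of the arm concerned.

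**Working it through.** **Inputs from the protocol's Statistical power section.** Up to 1,200 events in three equal arms (400 each), 10% attrition (360 each), within-child correlation 0.2 over 3 observations, intra-cluster correlation 0.02, control rate 65%, effects of 10 and 15 points, two-sided alpha 0.05. Recruitment is from at least 4 + 8 = 12 facilities (Recruitment section).

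**Stated power first.** No design-effect formula is given. One reconstruction, in which the catchment effect cancels between arms, is (1 − 0.2) + 3 × (0.2 − 0.02) = 1.34. Then 360 / 1.34 = 268.7 effective events per arm, and a pooled two-proportion test has power 71.7% and 97.5%, against the stated 72% and 98%. Using only the within-child term, 1 + 2 × 0.2 = 1.40, gives 360 / 1.40 = 257 and power 69.7% and 97.0%. The error rates below use 257; with 268.7 they barely move.

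**Bias.** Bias = share of a phase's events affected × drop in the on-time rate among them. Shares and drops are assumptions. If every affected child who would have been on time becomes late, the drop from the control rate is 65 points; a 30-point drop means that 0.30 / 0.65 = 46% of such children become late.

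| Assumption | Bias (points) | Phase 1 hit, no true effect: false-positive rate |
|---|---|---|
| 1 of 12 equal facilities for a whole phase, 30-point drop | 1/12 × 30 = 2.5 | 9% |
| 10% of events, 30-point drop | 0.10 × 30 = 3.0 | 11% |
| 1 of 12 facilities, all made late | 1/12 × 65 = 5.4 | 24% |
| 25% of events, 30-point drop | 0.25 × 30 = 7.5 | 41% |

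With 268.7 effective events, the 3.0- and 7.5-point rows become 11% and 43%.

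**Other direction.** If Phase 2 is hit and the true reminder effect is 10 points, a loss of 3 points cuts power from 70% to 40%, and a loss of 7.5 points cuts it to 9%.

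**What would mimic the whole planned effect.** A spurious 10 points needs 10 / 65 = 15.4% of Phase 1 events all made late, or 10 / 30 = one third of them at a 30-point drop.

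**Does a supply covariate help?** This was simulated with 360 children, three events each in one arm, within-child correlation 0.2, a logistic model with child-clustered standard errors, 600 runs per scenario, and 3% of events interrupted in the other phases.

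- Phase 1 hit (20% of events, half of the on-time ones made late), no true effect: the reminder odds ratio moves from 1.27 unadjusted to 1.00 adjusted, and false positives from 24% to 5%.
- Phase 2 hit in the same way, true odds ratio 1.62: the estimate moves from 1.18 to 1.61, and power from 15% to 66%.

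**Would a linear calendar-date term do instead?** Take events uniform in time, phases of length 1, no true effect, and a Phase 1 shock averaging 7.5 points but confined to one third of the phase (22.5 points there). With a common slope c, the reminder bias is 7.5 − c and the reminder-plus-incentive bias is 7.5 − 2c. The within-phase sum of squares is 3 × 1/12 = 0.25. A shock in the last third gives c = −(22.5 × 1/3 × 1/3) / 0.25 = −10; the first third gives +10; the middle third gives 0. The biases are then +17.5 / +27.5, −2.5 / −12.5 and +7.5 / +7.5 points. Such a term can worsen the bias.

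**The case against.** **The problem is disclosed and the covariate list is open.** Both are true. The Discussion names temporal change and supply failure, and the covariates are given only as examples. But the stated purpose of the list is participant characteristics, and the intention to address limitations commits to no analysis. A supply term chosen after the results are known would be discretionary. The gap is a narrow one: monitored data without a pre-specified use.

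**Most interruptions will not matter.** This stands in part. Only a deferral beyond 28 days changes the outcome, so a short outage does nothing, and interruptions spread evenly over the phases would largely cancel. The documents give neither frequency nor duration.

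**Rescheduling may absorb some delay.** The scheduling system and Study activities update later dates after a delay. Whether the primary outcome keeps the original due date is not stated. If the date is reset, part of the bias disappears and some events may move to a later arm.

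**Stronger readings that the documents do not support.**

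- A reader might infer that one local stock-out could create or cancel the whole planned effect. With at least 12 facilities, one equal-sized site gives at most about 5.4 points; 10 points needs a wider interruption.
- A reader might infer that each interruption hits one arm only. A 28-day window opened shortly before a transition runs into the next phase, so an interruption near a boundary can touch both.
- A reader might infer that the reference group is purely Phase 1. Later events without confirmed delivery are also coded 0. They are selected on non-delivery, however, and do not remove the confounding.

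**Conclusion.** The concern holds as a conditional one and should be dealt with before analysis. Arm is tied to calendar phase, late vaccination counts as failure whatever the cause, and the supply data that the trial plans to monitor enter no analysis. If interruptions are long enough to cross the 28-day limit and unequal between phases, the primary estimate is biased in a direction that depends on the phase affected.

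For the assumed shares and drops, the bias runs from about 2.5 to 7.5 points against a planned 10-point effect, with false-positive rates of about 9% to 41% in place of 5%. These figures illustrate scale and do not predict what will happen. They rest on assumed interruption rates, about 257 effective events per arm and, for the single-facility cases, equal-sized facilities. The documents do not show that such an interruption is likely, and nothing here establishes that the trial's result is biased.

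**What to change.** 1. State that the monitoring log records each interruption by facility, start and end date, and vaccine. The protocol says only that these events will be monitored.
2. Pre-specify in the primary model an event-level covariate: whether the child's facility was out of the due vaccine, or had sessions deferred by an outage, during the 28 days from the original due date. Use the full window for every event, whenever the child was vaccinated, and say that the original due date is the one that counts.
3. Leave mHealth and network failures out of this covariate, because they are part of delivering the intervention.
4. Add a sensitivity analysis that excludes affected events.
5. Do not rely on a linear calendar-date term for this purpose; as shown above, it can enlarge the bias from a transient shock.

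The cost is SAP wording, somewhat more structured logging, and linkage of the log to events by facility and date. The remedy has limits. It cannot separate an interruption that covers a whole phase at all facilities, and it does not remove other time trends, so the temporal limitation must stay in the conclusions.
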